#### **4.7 DISCONTINUATION OF SUBJECTS FROM STUDY**

Subjects must discontinue study treatment and withdraw from the study or optional sub-study for any of the following reasons:

- Withdrawal of informed consent (subject's decision to withdraw for any reason)
- PCa relapse at any time after completion of PROSTVAC administration (see 7.5 for definition)
- Any clinical adverse event (AE), laboratory abnormality, or intercurrent illness which, in the opinion of the investigator, indicates that continued participation in the study is not in the best interest of the subject
- Termination of the study by BNI
- Loss of ability to freely provide consent through imprisonment or involuntarily incarceration for treatment of either a psychiatric or physical (e.g., infectious disease) illness
- Initiation of any form of non-protocol cancer treatment
- Initiation of scheduled narcotics for pain treatment

- Unacceptable toxicity defined as any grade 3-4 possibly or definitely related non-hematologic toxicity that does not improve to grade 1 or resolve within 28 days or any possibly or definitely related grade 3-4 hematologic toxicity that does not improve to grade 1 or resolve with 14 days.

General or specific changes in the patient's condition render the patient unacceptable for further treatment in the judgment of the investigator.

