## 9.6 ASSESSMENT OF RELATIONSHIP TO STUDY DRUG (CAUSALITY)

Investigators are required to assess the causal relationship (i.e., whether there is reasonable possibility that the study drug caused the event) using the following definitions:

- **Unrelated:** Another cause of the AE is more plausible; a temporal sequence cannot be established with the onset of the AE and administration of the investigational product; or, a causal relationship is considered biologically implausible.
- **Possibly Related:** There is clinically plausible time sequence between onset of the AE and administration of the investigational product, but the AE could also be attributed to concurrent or underlying disease, or the use of other drugs or procedures. Possibly related should be used when the investigational product is one of several biologically plausible AE causes.
- **Definitely Related:** The AE is clearly related to use of the investigational product.

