We define an “interesting” reduction in the risk of relapse to be 30% (i.e., increase in the probability of RFS from 0.6 to 0.78). Assuming a one-sided alpha = 0.1, with 30 evaluable patients, we have 80% power to detect this difference based on an exact binomial test. Thus if among 30 evaluable subjects, at least 24 are recurrence free at 24 months, we will reject the null hypothesis (2 year RFS=0.60) and conclude that the PROSTVAC intervention improves RFS relative to the current standard of care in this patient population (one-sided p-value  $\leq 0.025$ ). Anticipating a final sample size of 30 patients with 10% drop out rate, we plan to enroll 33 patients for this study.

**Interim Analysis:** An interim analysis for futility will be performed through Simon’s minimax two-stage design (Simon, 1989) when a total number of 19 patients are evaluable. The design is described as follows:

**Stopping criteria:** Stop the study if there are 11 or fewer recurrence free among the first 19 evaluable patients. Otherwise, additional patients will be accrued resulting in a total evaluable sample size of 30.

**Decision rule at N=30 evaluable patients:** Reject the null hypothesis if there are 22 or more recurrence free among the 30 evaluable patients. We claim that the PROSTVAC intervention improves RFS relative to the current standard of care in this patient population. This design controls the type I error rate at 0.1 and yields the power of 0.8.

**Safety Monitoring:** Continuous safety monitoring will be performed with early stopping rules in the case of unacceptable risk to the subjects, defined as evidence in favor of a risk of a grade 3 or greater toxicity deemed to be possibly related to treated of 25% vs. an acceptable rate of 10%. Stopping criteria are shown in the table below. The stopping rules are based on a likelihood ratio. Specifically, the likelihood ratio is calculated based on a hypothesized 10% event rate (safe) vs, a 25% event rate (unsafe) and likelihood ratios in excess of 8 (in favor of an event rate of 25%)

are considered sufficient evidence to stop the trial. For example, 7 events in 33 patients yields an event rate of 0.21, which has a likelihood ratio of 9.21 favoring a rate of 25% vs. 10%.

Stop if:	Likelihood Ratio	Observed Event Rate
3 events in $\leq 6$ patients	$\geq 9.04$	$\geq 0.50$
4 events in $\leq 12$ patients	$\geq 9.08$	$\geq 0.33$
5 events in $\leq 18$ patients	$\geq 9.13$	$\geq 0.28$

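### The safety stopping rule in 10.1 names only possibly related toxicity, while 9.6 codes definitely related events separately and 4.7 names both; the plan should say which attributions count.

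*Combined protocol and SAP*

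**What the plan says.** The Safety Monitoring paragraph of section 10.1 sets up a continuous likelihood-ratio rule. The harm that it monitors is "a risk of a grade 3 or greater toxicity deemed to be possibly related to treated of 25% vs. an acceptable rate of 10" per cent. Evidence is sufficient to stop when there are "likelihood ratios in excess of 8 (in favor of an event rate of 25" per cent). The table gives boundaries of 3 events in up to 6 patients, 4 in up to 12, 5 in up to 18, 6 in up to 24 and 7 in up to 33.

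Section 9.6 has three attributions: unrelated, possibly related and definitely related. Possibly related is for events with other plausible causes besides the vaccine. The definition of definitely related is "The AE is clearly related to use of the investigational product".

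Section 4.7, on withdrawing an individual subject for unacceptable toxicity, uses the wording "any grade 3-4 possibly or definitely related non-hematologic toxicity", and names the same two categories again for hematologic toxicity.

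**The concern.** Section 9.6 defines possibly related as a category of its own, not as a floor that includes the stronger one. Whoever applies the boundary will count recorded attributions. Taken at its word, 10.1 selects one of the two related codes, and no other section says that the second is to be added. Section 4.7 shows that the protocol elsewhere writes out both.

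On that literal count, the events most securely tied to the vaccine would be missing from the trial-level rule. The error has one direction: the counted rate lies at or below the true related rate, so stopping comes later or not at all. The documents describe toxicities that could be attributed with confidence. PROSTVAC-V is replication-competent (5.1.1), and lesions away from the injection site are swabbed and tested (9.9.1). A severe, laboratory-confirmed vaccinia lesion would be a natural candidate for the definite category.

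**Working it through.** **Inputs from the documents (10.1).** Rates of 25% (unsafe) and 10% (acceptable); threshold LR > 8; the five printed boundary rows; 33 patients planned.

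**Input not in the documents.** The share f of related grade 3 or greater events that would be rated definite. It is an assumption, shown from 0 to 50%.

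**Step 1: reproduce the plan's likelihood ratios.** For x events in n patients,

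LR = (0.25/0.10)^x × (0.75/0.90)^(n−x).

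| Events / patients | LR printed (lower bound) | LR recomputed |
|---|---|---|
| 3 / 6 | 9.04 | 9.04 |
| 4 / 12 | 9.08 | 9.08 |
| 5 / 18 | 9.13 | 9.13 |
| 6 / 24 | 9.17 | 9.17 |
| 7 / 33 | 9.21 | 5.33 |

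The first four rows reproduce. The last does not. The plan states that "7 events in 33 patients yields an event rate of 0.21, which has a likelihood ratio of 9.21", but 2.5^7 × (0.75/0.90)^26 = 5.33, which is below 8. The printed 9.21 and the table's rate of 0.23 belong to 7 in 30; 7 in 31 already gives 7.68. This is a separate discrepancy. It matters here because it affects the baseline in Step 2, so that step is run both ways.

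**Step 2: probability of stopping.** The plan states none, so there is no printed figure to reproduce. Let p be the true rate of related grade 3 or greater toxicity, at most one counted event per patient, and q = p(1 − f) the rate that is counted on the literal reading. The probability of x counted events after n patients without having stopped follows

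P_n(x) = (1 − q)·P_(n−1)(x) + q·P_(n−1)(x − 1),

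and any mass at or above the boundary for that n is moved to stopped. The boundary is checked after each of the 33 patients.

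At p = 0.25:

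| Assumed definite share f | Counted rate q | P(stop), printed table | P(stop), LR > 8 at every n |
|---|---|---|---|
| 0% (or both categories counted) | 0.2500 | 0.789 | 0.737 |
| 5% | 0.2375 | 0.740 | 0.684 |
| 10% | 0.2250 | 0.685 | 0.626 |
| 20% | 0.2000 | 0.557 | 0.498 |
| 50% | 0.1250 | 0.158 | 0.136 |

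With the printed table, the loss relative to counting both is 0.789 − 0.740 = 0.049 at a 5% share, 0.104 at 10%, 0.232 at 20% and 0.631 at 50%.

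At p = 0.35 with the printed table, P(stop) is 0.977 at f = 0, then 0.964, 0.944, 0.880 and 0.416 at the same shares.

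**Step 3: cost of counting both.** At the acceptable rate, p = 0.10, with both categories counted, P(stop) is 0.073 with the printed table and 0.063 under LR > 8.

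**The case against.** The strongest reply is that 10.1 excludes nothing. It does not say that only possibly related events count, it does not cite 9.6, and it does not use the capitalised category name. In ordinary usage, toxicity deemed possibly related means possibly related or stronger. That reading fits a rule meant to detect unacceptable risk, and 4.7, by naming both categories, is evidence that the authors think inclusively. This stands. A reader might infer that the plan deliberately leaves the clearest vaccine toxicities out of the rule; the text does not support that.

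A reader might also infer that the rule loses much of its ability to stop. The documents do not support that either, because no section gives the definite share. Section 2.4.4.3 reports two serious events thought possibly due to the vaccine, both in one subject, and section 2.5 says that most attributable reactions were grade 1 or 2. Neither suggests a large share, though neither shows how severe events would be coded under 9.6 in this trial. If none are rated definite, nothing is lost.

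Finally, definitely related events are not unmonitored. Under 9.10 all serious adverse events reach the coordinating unit within 24 hours and are processed for the IRB, DSMC and FDA, and 4.7 acts on such events in the individual. This limits the practical consequence but does not replace the trial-level boundary, which is a count and needs a defined numerator.

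**Conclusion.** The mismatch is real and no other section resolves it: 10.1 names one related category, 9.6 has two, and 4.7 names both. It is an ambiguity in the definition of the stopping event, with the literal reading erring only toward not stopping.

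Its size is conditional. With the printed boundaries and a true related rate of 25%, the literal reading costs nothing if no severe events are rated definite, about 10 percentage points of stopping probability at an assumed 10% share, and about 63 points at 50%. The figures assume at most one counted event per patient, a check after each patient and all 33 patients treated. The 0.789 baseline uses the printed 7-in-33 row, which does not meet the plan's own threshold; under LR > 8 throughout, the baseline is 0.737 and the pattern of loss is similar.

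It should be clarified, because a safety boundary should not depend on how one word is read.

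**What to change.** State in 10.1 that the monitored event is grade 3 or greater toxicity assessed under 9.6 as possibly or definitely related, consistent with 4.7. If the sponsor intends anything else, 10.1 should say so and give the reason.

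The change takes a few words and leaves the rates, threshold and table as they are. The rule may trigger slightly more often than on the literal reading, with a probability of 0.073 at the acceptable 10% rate using the printed table. In the same edit, the last table row and the worked example should be reconciled with the likelihood-ratio formula and the threshold of 8.

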6 events in $\leq 24$ patients	$\geq 9.17$	$\geq 0.25$
7 events in $\leq 33$ patients	$\geq 9.21$	$\geq 0.23$

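### Last row of the safety stopping table conflicts with the plan's own criterion for 31 to 33 patients: 7 events in 33 give a likelihood ratio of 5.33, not 9.21

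*Combined protocol and SAP*

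**What the plan says.** The Safety Monitoring paragraph of section 10.1 sets up continuous monitoring of grade 3 or higher toxicity judged possibly related to treatment. It fixes the two rates to be compared: "the likelihood ratio is calculated based on a hypothesized 10% event rate (safe) vs, a 25% event rate (unsafe". It fixes the threshold too, treating "likelihood ratios in excess of 8 (in favor of an event rate of 25"%) as enough evidence to stop.

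The paragraph then illustrates the rule: "7 events in 33 patients yields an event rate of 0.21, which has a likelihood ratio of 9.21".

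The table below it has three columns: the stopping entry, the likelihood ratio and the observed event rate. The entries are:

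- "3 events in $\leq 6$ patients": ratio at least 9.04, rate at least 0.50
- "4 events in $\leq 12$ patients": ratio at least 9.08, rate at least 0.33
- "5 events in $\leq 18$ patients": ratio at least 9.13, rate at least 0.28
- "6 events in $\leq 24$ patients": ratio at least 9.17, rate at least 0.25
- "7 events in $\leq 33$ patients": ratio at least 9.21, rate at least 0.23

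The same section plans an enrolment of 33.

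**The concern.** The text and the table disagree before any likelihood is calculated. The worked example gives 7 of 33 a rate of 0.21, but the row that covers 33 patients says the rate is at least 0.23. Both cannot describe the same data.

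At stake is whether a pre-specified toxicity rule gives one answer. If the seventh event falls on patient 31, 32 or 33, a reader who follows the row's stopping entry stops. A reader who calculates the ratio and applies the threshold does not. The worked example, which is there to show how the rule works, credits this result with more evidence than the data carry.

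**Working it through.** **Inputs, all from section 10.1:** safe rate 0.10, unsafe rate 0.25, threshold 8, the five table rows, and planned enrolment of 33.

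**Formula.** For k events in n patients, the likelihood ratio for two fixed binomial rates is

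LR = (0.25/0.10)^k × (0.75/0.90)^(n−k) = 2.5^k × 0.8333^(n−k)

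**Step 1: reproduce the plan's figures.** The second ratio column adds one more patient without an event.

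| Events | Row limit n | LR at n | Printed | LR at n+1 |
|---|---|---|---|---|
| 3 | 6 | 9.04 | 9.04 | 7.54 |
| 4 | 12 | 9.08 | 9.08 | 7.57 |
| 5 | 18 | 9.13 | 9.13 | 7.61 |
| 6 | 24 | 9.17 | 9.17 | 7.64 |

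The formula matches rows 1 to 4. In each, the limit is the largest n at which the ratio still exceeds 8. The limits rise by six patients per row.

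**Step 2: the last row and the worked example.**

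- 7 of 33: 2.5^7 × 0.8333^26 = 610.35 × 0.0087355 = 5.33; rate 7/33 = 0.212
- 7 of 30: 2.5^7 × 0.8333^23 = 610.35 × 0.0150949 = 9.21; rate 7/30 = 0.233

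The printed 9.21 and 0.23 are therefore the values for n = 30, which is also the next step after 24 in the row pattern.

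**Step 3: where the row fails.**

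| n with 7 events | LR | Observed rate | LR above 8? |
|---|---|---|---|
| 30 | 9.21 | 0.233 | yes |
| 31 | 7.68 | 0.226 | no |
| 32 | 6.40 | 0.219 | no |
| 33 | 5.33 | 0.212 | no |

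For n of 30 or fewer, the row meets the criterion. For comparison, 8 events in 33 give 2.5^8 × 0.8333^25 = 15.995.

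**Step 4: other readings of the ratio.** Using the observed rate in place of 25% gives 6.08 for 7 of 33. The ratio of the exact upper-tail probabilities of 7 or more events gives 18.06. Neither gives 9.21.

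**Step 5: effect on the rule.** The stopping probabilities below are exact, from a patient-by-patient recursion to n = 33. The first line follows the table's stopping entries. The second stops whenever LR exceeds 8, which over this range means 7 events by patient 30 or 8 by patient 33 after the first four rows.

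| Rule | True rate 10% | 15% | 25% |
|---|---|---|---|
| Table as printed | 0.0733 | 0.2770 | 0.7889 |
| LR above 8 throughout | 0.0635 | 0.2391 | 0.7366 |
| Difference | 0.0098 | 0.0379 | 0.0523 |

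The chance that the conflict arises at all is the chance that the seventh event falls on patients 31 to 33 with no earlier stop. It is the printed table's stopping probability minus that of the same table with its last row ended at 30:

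- At 10%: 0.0733 − 0.0626 = 0.0107
- At 15%: 0.2770 − 0.2333 = 0.0437
- At 25%: 0.7889 − 0.7209 = 0.0680

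**The case against.** The best defence is that the discrepancy is narrow and errs on the cautious side. It needs exactly 7 events, with the seventh on one of the last three planned patients. At the acceptable 10% rate it adds about one percentage point to the chance of stopping, and it does not touch the primary endpoint, the sample size or the efficacy decision rule. All of that stands. It bears on how serious the error is, not on whether it is one.

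A second defence is that the limit of 33 may be deliberate: the team may have extended the last row to full enrolment and left the ratio and rate from n = 30 in place. The documents do not settle this. Even so, the printed ratio is wrong for 7 of 33, and the extended row does not meet the threshold stated just above it.

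Three stronger readings are tempting, and the documents do not support them:

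- **That subject protection is weakened.** The stopping entry leads to stopping sooner than the criterion would, not later.
- **That the table would certainly stop the trial at 7 of 33.** The row also prints a ratio of at least 9.21, which 7 events fail at 31, 32 and 33 patients. The instruction is contradictory, and the outcome depends on which column is treated as binding.
- **That the safety committee would be given a false ratio of 9.21.** Sections 9.10 and 11.1 have adverse events and serious breaches reported to that committee. Nothing says a likelihood ratio is reported to it.

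**Conclusion.** The error is established. With both rates and the threshold fixed by the plan, 7 events in 33 patients give a likelihood ratio of 5.33 at a rate of 0.21, and 5.33 does not exceed 8. The conflict is confined to 7 events at 31, 32 or 33 patients.

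It raises the probability of stopping by about 1 percentage point at a true rate of 10%, 4 points at 15% and 5 points at 25%, if the stopping entry is taken as binding. These probabilities assume independent patients with a common event rate, outcomes known one patient at a time, and monitoring that ends at 33. Section 4.1 gives a total of 44 subjects, a number that the table does not reach. The ratios themselves need none of the assumptions about monitoring.

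A reader might go on to infer that the row was meant to end at 30. The row pattern and the printed values are consistent with that, but the worked example also says 33, so the documents do not show which figure was intended.

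**What to change.** Reconcile the last table row, the worked example and the threshold of 8 so that they give one instruction. Two forms are internally consistent:

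- **The row limit follows the stated criterion.** With 7 events the ratio exceeds 8 only up to n = 30 (9.21, rate 0.23). At n = 33, 8 events give 15.995.
- **The 7-in-33 row stays.** It would then show its true ratio of 5.33 and rate of 0.21, and the text would state that a lower evidence threshold applies to that row.

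The choice between them is the sponsor's, and this review does not recommend either. The likelihood ratio in the worked example must be corrected in both cases. The cost is one table row and one sentence, plus a statement of the lower threshold if the second form is chosen. No new data are needed.

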## 10.2 SECONDARY OBJECTIVES

### 10.2.1 Comparison of Observed RFS with Predicted RFS

A secondary endpoint will be a comparison of the observed RFSs with the predicted (“virtual”) RFS for the same patients based on clinical and pathologic information collected at baseline. The predicted RFSs will be constructed with published and validated algorithms (Duke and CaPSURE). The observed RFSs of the treated subjects are compared with the predicted RFSs as if the same subjects had not been treated. The comparison is performed using the logrank test of the observed and predicted RFSs. These represent the estimated RFSs for patients with those clinical characteristics if they did not receive any adjuvant therapy.

RFSs will be displayed graphically using Kaplan-Meier curves. We then use the log rank test to compare the virtual or estimated RFSs values of the test patients with the observed values following PROSTVAC-V/F.

The comparative analysis (observed vs predicted RFS) will be performed repeatedly during the course of the study, whenever an additional 5 subjects relapse or reach the end of the 2-year follow up period.

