#### **3.2 SECONDARY OBJECTIVES**

There are four secondary objectives.

- To compare observed RFSs for the study population with the predicted RFSs for the study population. The predicted RFS values will be calculated from each patient's clinical and pathologic data by standard algorithms (Duke and CaPSURE). The observed and predicted RFSs will be presented as Kaplan-Meier plots and comparisons will be performed using the logrank test.
- To compare the observed RFS with the RFSs of a historical comparison group of MUSC prostatectomy patients. These patients will be matched to the experimental group for race, Gleason score, and pathological stage. The observed, historical RFSs will be presented as Kaplan-Meier plots and comparisons will be performed using the logrank test.
- To describe associations between the RFS values and various immunologic, genetic, and biochemical parameters on research blood and tissue specimens.
- To describe the toxicity of PROSTVAC-V/F in this patient population.

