### 10.2.3 Correlative Laboratory Studies

Biochemical and genomic measurements will be summarized both graphically and numerically using descriptive statistics. Transformations will be performed based on the observed distribution of the endpoints. Cox regression will be used to estimate hazard ratios measuring the association between these measures and RFS. 95% confidence will be estimated for the hazard ratios as appropriate.

For the amount of antibody forcement antigen, graphical displays such as scatterplots of optical density of particular color and dilution will be made for pre- and post-vaccination. To investigate if the distributions of pre- and post-vaccination are different, Kolmogorov-Smirnov test will be performed. The reverse sigmoidal curves will fit to estimate model parameters such as slope and 50% of maximum effect for the antibody measurement. Depending on the curve results, different percentages of maximum effect (e.g., 65-75%) will be investigated as well. Moreover, those interest of immune parameters will be compared between pre- and post-vaccination. The

difference of the immune parameters will be used for measuring the association between these measures and time to relapse/stress.

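### The log-rank of observed against predicted RFS treats predictions for the same men as a second sample and is repeated without error control, and the pre/post antibody test ignores pairing (secondary and correlative analyses only)

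*Combined protocol and SAP*

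**What the plan says.** Section 10.2.1 sets up "a comparison of the observed RFSs with the predicted (“virtual”) RFS for the same patients", with the predictions taken from the Duke and CaPSURE algorithms. The test is given as: "The comparison is performed using the logrank test of the observed and predicted RFSs". Section 3.2 repeats it: "The observed and predicted RFSs will be presented as Kaplan-Meier plots and comparisons will be performed using the logrank test". The synopsis and Section 7.5.2 also name a log-rank test. No place names a one-sample, stratified or paired form, and none says how a predicted probability becomes a predicted time.

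On repetition, Section 10.2.1 says: "The comparative analysis (observed vs predicted RFS) will be performed repeatedly during the course of the study", the trigger being "whenever an additional 5 subjects relapse or reach the end of the 2-year follow up period". It gives no significance level, adjusted boundary or statement that these looks are descriptive.

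On the antibody assay, Section 10.2.3 says: "To investigate if the distributions of pre- and post-vaccination are different, Kolmogorov-Smirnov test will be performed". Section 8.1.2 shows that these are serial samples from the same subjects: before treatment, after the third injection and after the last. Section 10.2.3 uses the within-man difference only for association with relapse or stress.

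**The concern.** A prediction computed from a man's baseline data is a reference value. It is not an outcome from a second man. A two-sample log-rank gives the predicted curve sampling variance it may not have and ignores the fact that each prediction belongs to one of the observed men. Both errors tend to make the test conservative. Repeating it without adjustment pushes the error rate up. The size of the resulting p-value then depends on a construction that the plan does not describe.

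At stake is the first-listed secondary objective, which adjusts for each man's own clinical and pathologic risk. In a single-arm trial of 30 men, power lost here is hard to recover. The antibody test has the simpler fault of discarding the pairing.

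**Working it through.** **The plan's own figures.** Section 10.1 states type I error 0.1 and power 0.8 for the two-stage rule (stop at 11 or fewer of 19; reject at 22 or more of 30). Exact binomial calculation gives 0.093 and 0.801, so that rule reproduces. The plan states no operating figures for the log-rank or Kolmogorov-Smirnov tests.

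**Inputs from the protocol.** 2-year RFS is 0.60 (null) and 0.78 (target); with exponential times HR = ln 0.78 / ln 0.60 = 0.486. On numbers: "Anticipating a final sample size of 30 patients with 10% drop out rate, we plan to enroll 33 patients for this study". Looks: 30/5 = 6 (33/5 = 6.6).

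**Assumptions not in the documents.** Two-sided 5%; uniform 18-month accrual; between-man SD of log hazard 0 to 1.5; virtual times either drawn at random from the predictions or fixed at quantiles of the mean predicted curve. There were 3,000 null and 2,000 alternative replicates.

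**Null rejection, nominal 0.05**

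| Virtual times | SD | Two-sample, one look | Two-sample, six looks | One-sample, one look | One-sample, six looks |
|---|---|---|---|---|---|
| drawn | 0 | 0.054 | 0.118 | 0.052 | 0.143 |
| drawn | 0.5 | 0.045 | 0.107 | 0.057 | 0.151 |
| drawn | 1.0 | 0.025 | 0.071 | 0.061 | 0.164 |
| drawn | 1.5 | 0.011 | 0.042 | 0.056 | 0.150 |
| fixed | 0 | 0.006 | 0.034 | 0.051 | 0.145 |
| fixed | 0.5 | 0.003 | 0.027 | 0.049 | 0.147 |
| fixed | 1.0 | 0.0007 | 0.016 | 0.054 | 0.142 |
| fixed | 1.5 | 0.0003 | 0.015 | 0.061 | 0.146 |

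Hand check of the fixed row at SD 0: only one of the two arms varies, so the true variance is about half the nominal one. The rejection rate is then about P(|N| > 1.96/√0.5) = P(|N| > 2.77) = 0.006, as simulated.

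**Power at 2-year RFS 0.78, one look**

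| Virtual times | SD | Two-sample | One-sample |
|---|---|---|---|
| drawn | 0 | 0.34 | 0.50 |
| drawn | 1.0 | 0.22 | 0.52 |
| fixed | 0 | 0.29 | 0.49 |
| fixed | 1.0 | 0.15 | 0.51 |

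Hand checks:
- Two-sample: events = 30 × 0.22 + 30 × 0.40 = 18.6. Power = Φ(√(18.6/4) × |ln 0.486| − 1.96) = Φ(−0.41) = 0.34.
- One-sample, Z = (O − E)/√E: mean O = 6.6 and mean E = 6.6/0.486 = 13.6, so mean Z = −7.0/3.68 = −1.9 and power is roughly one half.

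**Repeated looks alone.** One million null paths with six equally spaced looks give an overall error of 0.154 for a correctly sized test. A Pocock boundary would need p of about 0.014 at each look.

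**Antibody test.** 30 pairs, shift of 0.5 SD, 6,000 replicates:

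| Assumed correlation | K-S null | K-S power | Signed-rank null | Signed-rank power |
|---|---|---|---|---|
| 0 | 0.035 | 0.31 | 0.053 | 0.45 |
| 0.5 | 0.007 | 0.28 | 0.046 | 0.74 |
| 0.7 | 0.0015 | 0.24 | 0.052 | 0.92 |

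A separate simulation at correlation 0.5 gave 27% for Kolmogorov-Smirnov and 74% for signed-rank.

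**The case against.** **The test form is inferred.** The documents say only log-rank. The protocol cites a published method for virtual control groups in single-arm trials (reference 122), which cannot be consulted here. This stands as a limit. Two Kaplan-Meier curves with an unqualified log-rank still read most naturally as a two-sample test, and if another form is meant the plan should say so.

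**The conservatism is conditional.** With randomly drawn virtual times and no heterogeneity, the two-sample test holds its size (0.054). That stands, but even then its power is 0.34 against 0.50.

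**A one-sample test has its own weakness.** It takes the predictions as correct. Section 10.1's two control sources give 2-year RFS of 0.645 and 0.56. If predictions averaged 0.56 and the truth were 0.645, mean O = 30 × 0.355 = 10.65 and mean E = 10.65 × ln 0.56 / ln 0.645 = 14.1. The ratio is 0.76 with no vaccine effect, and simulated rejection is 12-15%, nearly always favouring the vaccine. This stands and must be stated with the result. Changing the test does not cure poor calibration.

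**Kolmogorov-Smirnov looks for any change in distribution.** A pure shift favours signed-rank. This is true, but its null rejection of 0.007 at correlation 0.5 shows that the pairing is being ignored.

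**Stronger readings that a reader might infer.** One is that the plan's false-positive rate is about 15%. That figure is for a correctly sized test, whereas the planned form gives about 2-12%. Another is that the trial's main conclusion is compromised. Section 10.1 bases it on a binomial count, keeps time-to-event RFS out of the primary inference, and ties no stopping decision to these looks. A third is that the main evidence of vaccine activity is mishandled. The Kolmogorov-Smirnov sentence concerns the anti-Forssman assay, which Section 8.1.2 says may reflect general immune activation. The PSA-specific T-cell assays in Section 8.1.1 are separate.

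**Conclusion.** The point holds for secondary and correlative analyses, and the change should be made. Read as a two-sample test, a single final log-rank has null rejection from about 6% down to 0.3% or less at nominal 5%, and power of 15-34% where a one-sample log-rank with well-calibrated predictions has about 50%. Six unadjusted looks bring the net error to about 2-12%. Where in that range it falls depends on how virtual times are built and how much risk varies between men, and the plan gives neither. The Kolmogorov-Smirnov test has null rejection of about 0.7% and power of about 27%, against 74% for signed-rank, for a 0.5 SD shift at an assumed correlation of 0.5.

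The figures rest on exponential times, two-sided 5%, 30 men and six looks. Section 4.1 gives 40 evaluable subjects, which would mean 40/5 = 8 looks; the two counts need reconciling. Using both nomograms adds a further source of multiplicity not included above.

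**What to change.** 1. **Test.** Specify a one-sample log-rank of observed relapses against expected relapses, summed from each man's predicted cumulative hazard. State how that hazard is obtained from the nomogram output.
2. **Time origin and event rules.** Use those of observed RFS, which runs from surgery. An enrolled man cannot have relapsed before enrolment, and a PSA relapse counts only after all doses, although other events can count sooner. Expected events must allow for both. Treatment may start up to 120 days after surgery. At a constant hazard with 2-year RFS 0.60, charging those days would add up to 30 × (120/730) × 0.511 = 2.5 expected relapses that could not be observed. With the last dose on Day 141, PSA relapse may not count until 120 + 140 = 260 days after surgery.
3. **Nomograms.** Name one as main and the other as sensitivity.
4. **Timing.** Test once, when all men have reached 2 years, and show interim curves without p-values.
5. **Reporting.** Give the observed/expected ratio with its confidence interval and state that it depends on nomogram calibration.
6. **Antibody.** Replace Kolmogorov-Smirnov with a Wilcoxon signed-rank test on each man's change in log titre at one named post-vaccination time point.

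The cost is SAP wording and a small amount of programming. No extra patients, visits or samples are needed.
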